5.2 Treatment Compliance

Treatment compliance will be assessed via direct observation by the Study Investigator who is responsible for study drug administration. The exact time of injection will be recorded in the CRF.

5.3 Supportive Care/Prohibited Treatments

Subjects will receive supportive measures as determined by their needs and according to the accepted standards of care. All subjects will be treated with ophthalmic corticosteroid eye drops (prednisolone acetate ophthalmic suspension) to minimize any inflammation for 7 days starting on the day of injection, with a decision by the Study Investigator at the Day 7 visit regarding whether/when to taper the Predforte or to switch to a different medication. If extended beyond 7 days, the reason for longer treatment should be documented. Cyclogyl, one drop twice daily, may also be given to the treated eye for 7 days. Upon day 7 examination, the Investigator will determine whether the drop can be discontinued depending on the exam findings. The Cyclogyl will cause dilation of the affected eye. This may result in light sensitivity or a brief burning sensation after instillation of the drop, but should not be a significant burden for subjects. The prohibited treatments are any immunosuppressant other than topical steroids as noted above.

6.0 STUDY EVALUATIONS

Where indicated below, some study assessments will be performed at the jCyte Low Vision facility at baseline, and at 6 and 12 months post-treatment.

6.1 Screening

- a. informed consent
- b. prior participation in jCell study; subject must have completed the prior study through the 12 month follow up visit.
- c. updated medical history and physical exam, including vital signs, height, weight and detailed ocular medical history including any previously undocumented history of eye diseases or disorders other than RP
- d. pregnancy test, if female
- e. CBC, platelet, differential, hemoglobin, hematocrit
- f. blood chemistries, not limited to, but must include AP, ALT, AST, BUN, Cr, total bilirubin, serum electrolytes, glucose, calcium, phosphate, albumin and total protein
- g. urinalysis
- h. slit lamp and fundus exam
- i. BCVA

6.2 Baseline

The assessments (indicated by an asterisk*) do not need to be repeated if Day 0 (treatment day) is within 30 days of screening. Subjects should be advised to discontinue daily aspirin or clopidogrel regimens for 5 days prior to study treatment.

Performed at clinical study site at baseline

- a. Updated medical history and physical exam*, including height, weight, and detailed ocular medical history including any previously undocumented history of eye diseases or disorders other than RP
- b. vital signs
- c. pregnancy test, if female*
- d. hematology [CBC, platelet, differential, hemoglobin, hematocrit]*
- e. blood chemistries*, not limited to, but must include AP, ALT, AST, BUN, Cr, total bilirubin, serum electrolytes, glucose, calcium, phosphate, albumin and total protein
- f. urinalysis*
- g. slit lamp, fundus exam
- h. Optos photography
- i. BCVA
- j. IOP
- k. OCT (performed at site and sent to central reading lab for analysis)
- 1. blood sample for Ab testing

Performed at jCyte low vision facility at baseline

- m. VF
- n. Contrast Sensitivity
- o. Mobility test
- p. Optional exploratory ophthalmic imaging: ultrasound imaging (ultrasound biomicroscopy, ultrasound A- and B-scan), additional variants of slit lamp biomicroscopy with photography/videography using gonioscopy lens, optical coherence tomography (OCT) of jCells and/or retinal sensitivity with full-field sensitivity threshold testing (FST)

6.3 Day 0

Before administration of jCell (Day 0)

- a. vital signs, within 15 minutes prior to injection
- b. BCVA
- c. IOP

After administration of a single intravitreal dose of jCell

- a. exact dose and time of injection ; any dose interruption must be documented
- b. vital signs at 15 and 60 minutes after treatment or until returned to pre-treatment levels
- c. intraocular pressure by tonometry post-treatment must be ≤30 mm Hg prior to patient release
- d. verify basic vision by lights, hand motions and fingers, depending upon individual patient's baseline prior to patient release
- e. con meds
- f. adverse events

6.3.1 Day 1 (24 hours)

- a. brief medical history and physical exam, including any change in vision or light perception reported by patient or noted by study staff not specifically assessed (for example, patient reports that general vision is "brighter" or study staff reports that patient response to certain assessments seems more rapid)
- b. vital signs
- c. slit lamp and fundus exam
- d. Optos photography
- e. BCVA
- f. IOP
- g. con meds
- h. adverse events

6.3.2 **Day 7 (week one)**

- a. brief medical history and physical exam, including any changes in vision or light perception reported by patient or noted by study staff since prior MH & PE
- b. vital signs
- c. BCVA
- d. IOP
- e. con meds
- f. adverse events

Performed at jCyte low vision facility one week post-treatment (optional)

g. exploratory ophthalmic imaging: ultrasound imaging (UBM, A- and B-scan), additional variants of slit lamp biomicroscopy with photography/videography using gonioscopy lens, OCT of jCells.

6.3.3 Day 28 (week four/month 1) +/- 1 day

- a. brief medical history and physical exam, including any changes in vision or light perception reported by patient or noted by study staff since prior MH& PE
- b. vital signs

- c. CBC, platelet, differential, hemoglobin, hematocrit
- d. blood chemistries, not limited to, but must include AP, ALT, AST, BUN, Cr, total bilirubin, serum electrolytes, glucose, calcium, phosphate, albumin and total protein
- e. slit lamp and fundus exam
- f. Optos photography
- g. BCVA
- h. IOP
- i. con meds
- j. adverse events
- k. blood sample for Ab testing

Performed at jCyte low vision facility day 28 post-treatment (optional)

1. exploratory ophthalmic imaging: ultrasound imaging (UBM, A- and B-scan), additional variants of slit lamp biomicroscopy with photography/videography using gonioscopy lens, OCT of jCells.

6.3.4 Month 3 (Day 90) +/- 4 days

- a. brief medical history and physical exam, including any changes in vision or light perception reported by patient or noted by study staff since prior MH & PE
- b. vital signs
- c. CBC, platelet, differential, hemoglobin, hematocrit
- d. blood chemistries, not limited to, but must include AP, ALT, AST, BUN, Cr, total bilirubin, serum electrolytes, glucose, calcium, phosphate, albumin and total protein
- e. urinalysis
- f. slit lamp and fundus exam
- g. Optos photography
- h. BCVA
- i. IOP
- j. con meds
- k. adverse events

Performed at jCyte low vision facility at 3 months post-treatment (optional)

h. exploratory ophthalmic imaging: ultrasound imaging (UBM, A- and B-scan), additional variants of slit lamp biomicroscopy with photography/videography using gonioscopy lens, OCT of jCells and/or retinal sensitivity with FST.

6.3.5 Month 6 (Day 180) +/- 4 days

Performed at clinical study site 6 months post-treatment

- a. brief medical history and physical exam, including any changes in vision or light perception reported by patient or noted by study staff since prior MH & PE
- b. vital signs
- c. CBC, platelet, differential, hemoglobin, hematocrit
- d. blood chemistries, not limited to, but must include AP, ALT, AST, BUN, Cr, total bilirubin, serum electrolytes, glucose, calcium, phosphate, albumin and total protein
- e. urinalysis
- f. slit lamp and fundus exam
- g. Optos photography
- h. BCVA
- i. IOP
- j. con meds
- k. adverse events
- 1. blood sample for antibody testing

Performed at jCyte low vision facility 6 months post-treatment

- m. VF
- n. Contrast Sensitivity
- o. Mobility test
- p. optional exploratory ophthalmic imaging: ultrasound imaging (UBM, A- and Bscan), additional variants of slit lamp biomicroscopy with photography/videography using gonioscopy lens, OCT of jCells and/or retinal sensitivity with FST.

6.3.6 Month 9 (Day 270) +/- 4 days

- a. brief medical history and physical exam, including any changes in vision or light perception reported by patient or noted by study staff since prior MH & PE
- b. vital signs
- c. slit lamp and fundus exam
- d. Optos photography
- e. BCVA
- f. IOP
- g. con meds
- h. adverse events

Performed at jCyte low vision facility 9 months post-treatment (optional)

i. exploratory ophthalmic imaging: ultrasound imaging (UBM, A- and B-scan), additional variants of slit lamp biomicroscopy with photography/videography using gonioscopy lens, OCT of jCells.

6.3.7 End of Treatment (Month 12) or Early Termination Visit +/- 10 days

Performed at clinical study site 12 months post-treatment

- a. MH and physical exam, including weight and height
- b. vital signs
- c. pregnancy test (if applicable)
- d. CBC, platelet, differential, hemoglobin, hematocrit
- e. blood chemistries, not limited to, but must include AP, ALT, AST, BUN, Cr, total bilirubin, serum electrolytes, glucose, calcium, phosphate, albumin and total protein
- f. urinalysis
- g. slit lamp and fundus exam
- h. Optos photography
- i. BCVA
- j. IOP
- k. OCT (performed at site and sent to central reading lab for analysis)
- l. con meds
- m. adverse events

Performed at jCyte low vision facility 12 months post-treatment

- n. VF
- o. Contrast Sensitivity
- p. Mobility test
- q. optional exploratory ophthalmic imaging: ultrasound imaging (UBM, A- and Bscan), additional variants of slit lamp biomicroscopy with photography/videography using gonioscopy lens, OCT of jCells and/or retinal sensitivity with FST.

7.0 ASSESSMENTS

7.1 Safety Assessments

7.1.1 Adverse Events

Subjects will be monitored for AEs from the time the subject receives a subject number until the study end or early termination. Adverse events that occur between clinic visits will be elicited by direct, non-leading questioning or will be recorded if offered voluntarily by the subject. Further details for AE reporting can be found in Section 9.

7.1.2 Vital Signs

Blood pressure and heart rate, body temperature and respiratory rate will be recorded at screening, before and after intravitreal injection and at all follow-up visits.

7.1.3 Clinical Laboratory Tests

Blood samples for clinical laboratory tests will be taken as indicated in Table 2.

Hematology – full blood count including red blood cell (RBC) count, hemoglobin, hematocrit, white blood cell (WBC) count with differential and platelet count; neutrophils, lymphocytes, monocytes, eosinophils, basophils.

Biochemistry – alanine aminotransferase (ALT), aspartate aminotransferase (AST), alkaline phosphatase (AP), blood urea nitrogen (BUN), creatinine, total bilirubin, serum electrolytes, glucose, calcium, phosphate, albumin and total protein

Urinalysis – pH, protein, ketones, glucose, bilirubin, blood, urobilinogen, specific gravity by dipstick and microscopy if any findings are abnormal.

Pregnancy A urine sample will be collected for a pregnancy test at screening for female subjects of childbearing potential to test for pregnancy. If this is found to be positive, it will be followed up with a serum pregnancy test.

7.1.4 Blood Samples for Antibody Testing

Blood samples will be collected for testing for Panel Reactive Antibodies (PRA) and Donor Reactive Antibodies (DRA) from subjects prior to treatment, at 4 weeks post-treatment, and at 6 months post-treatment. Details of preparation/shipping of samples will be provided separately.

7.1.5 **Ophthalmic AEs**

Procedures will be performed at scheduled intervals to specifically assess eye AEs that may not be detected by usual AE reporting and to try and visualize the injected cells. Please refer to the study procedure manual for details of all ophthalmologic assessment procedures.

Slit lamp and fundus exam - The binocular slit-lamp examination provides a stereoscopic magnified view of the eye structures in detail, enabling anatomical diagnoses to be made for a variety of eye conditions. This assessment will include detection of anterior chamber cell or flare; acute cataract development or progression in phakic patients, or vitreous haze. Fundus exam allows for inspection of the retina, the cellular graft, and detection of retinal detachment.

Optos photography - Optos photography includes a widefield dilated Optos photograph of the posterior segment with any cell cluster from the anterior vitreous visualized in the photo frame along with the posterior segment/fundus.

IOP - Intraocular pressure is measured with a tonometer as part of a comprehensive eye examination. Measured values of intraocular pressure are influenced by corneal thickness and rigidity

7.2 Efficacy Assessments

7.2.1 Please strictly adhere to the study procedure manual for details of all ophthalmologic assessment procedures.

7.2.2 Spectral Domain Optical Coherence Tomography (OCT) (performed locally and read centrally)

A clinical OCT machine will be used for data collection; the same machine should be used for any given patient at each time point. OCT results will be sent to a central reading lab for assessment.

7.2.3 Mobility Testing (performed at jCyte Low Vision Facility)

In general, the mobility test will consist of differing but structurally similar configurations of a relatively short maze (e.g. arrows on a printed floor mat) with ten obstacles, of various sizes. Subject testing consists of walking through several configurations each at a different illumination level as a test of mesopic visual function. Each test is videotaped and scored for speed and accuracy (number of errors) by masked independent trained graders and a score, the critical illumination level (CIL), is derived from the illumination level at which a significant drop in functional performance is observed (slow walking speed and increase in errors). For subjects assessed during the baseline testing who have an estimated monocular CIL of 1 lux or lower (near normal vision), they will be tested with that eye on both a high contrast (black and white) and a low contrast version (either 25% or 10% light grey arrows) at baseline and each low vision visit. A larger range of testing improvement should occur in the low contrast version, allowing for greater test sensitivity (i.e., preventing a ceiling effect) if the subject's vision improves with treatment.

7.2.4 BCVA (E-ETDRS) (performed at the clinical site)

BCVA will be tested at scheduled time points in both eyes in all subjects. Visual acuity will be measured with the electronic visual acuity testing algorithm (E-ETDRS) for eyes with vision better than 20/800. The measurements will be taken using a single line testing strategy with two measurements per eye at each study visit. In the event that the two measurements differ by more than seven letters, then a third measurement will be taken. For any individual eye that cannot be tested with the electronic visual acuity testing algorithm (E-ETDRS), a score of 0 letters will be used.

Trial frame refraction is the gold standard in obtaining the most accurate refractive error in low vision patients. It involves the use of a trial frame, loose lenses and specialized low vision eye charts that are different from the eye charts used in a regular eye examination. These special low vision eye charts contain different-sized letters or numbers that can help determine the sharpness or clarity of the subject's distance vision. Performed properly, the examiner obtains not only the refractive error, but additional potentially essential information, such as the level and quality of visual acuity, sensitivity to blur, effects of glare CONFIDENTIAL 28 of 37 and the quality of fixation. The optical theory involved is the same as when refracting the normal eye, but special adjustments in lens selection, presentation strategy, and "just noticeable difference", are incorporated for low vision patients. These adjustments usually include large lens increments and special techniques for exploring and refining cylinders.

7.2.5 Visual Field Testing (performed at jCyte Low Vision Facility)

Subjects enrolled in the study may have a severely restricted visual field (e.g., 4 degrees in diameter) with or without eccentric islands in the mid to far-periphery in advanced RP, or they may have full visual fields but reduced photopic sensitivity in earlier stages of RP. The Octopus 900 will be used for kinetic visual field testing using a specified target of V4e for more severe subjects and a target of III4e and V4e for better seeing subjects. Target size will be selected based on baseline visit for each eye separately. Whatever target size(s) is/are selected, the same size will be used throughout the study on that particular eye.

7.2.6 Contrast Sensitivity (performed at jCyte Low Vision Facility)

A contrast sensitivity test measures the ability of a subject to distinguish between finer and finer increments of light versus dark (contrast). Contrast provides critical information about edges, borders, and variations in luminance. Contrast sensitivity is correlated to performance on many real world tasks and tests that generate a curve or multiple sensitivity thresholds at varying grating sizes (spatial frequency) provide an in-depth view of functional vision. Using the Beethoven System, multiple thresholds and varying spatial frequencies creating a curve will be measured monocularly and the peak of the curve compared over time. Each spatial frequency is tested up to four times (thresholds) so the mean threshold at the peak contrast sensitivity for each eye will be compared over time.

7.3 Exploratory Assessments

7.3.1 Ultrasound Biomicroscopy (UBM) (performed at jCyte Low Vision Facility)

With an same ultrasound instrument as for A and B-scans, but using a different probe for UBM, high frequency high-resolution images of the cross-sectional anterior chamber can be acquired. UBM will be used to explore a more thorough volume estimation by ultrasound imaging of the jCell aggregate over time.

7.3.2 B-Scan (performed at jCyte Low Vision Facility)

B-scan ultrasound uses high-frequency sound waves to obtain measurements and produce detailed images of the eye. In the area of the typical IVT injection site, two probe directions (perpendicular to the corneal surface and inferotemporal) will be used to locate jCells.

This test may provide information regarding the location of the injected cells and the general size of the cell clusters at different time points post-treatment.

7.3.3 A-Scan (performed at jCyte Low Vision Facility)

A-scan ultrasound also uses high-frequency sound waves to obtain measurements of the length of the eye and the size of the jCell aggregate. These measurements can be used to support calculations that may be needed in exploratory analysis. With such corrections from A-scans, more precise volume estimation of the jCells may be achieved.

7.3.4 Slit lamp biomicroscopy with gonioscopy lens & photography (performed at jCyte Low Vision Facility)

Binocular slit-lamp biomicroscopy provides a stereoscopic magnified view of eye structures, enabling general anatomical exploration of the jCell aggregate over time. When combined with a gonioscopy contact lens (three-mirror lens with gel between the lens and cornea), a greater viewing angle into the anterior vitreous behind the iris to view and photograph/videograph jCells can be achieved. Photography and/or video recording through the gonioscopy lens will be used as a means to explore the shape and size of the jCell aggregate over time.

7.3.5 Hyperspectral OCT (whole eye) (performed at jCyte Low Vision Facility)

Standard SD-OCT imaging is primarily used for image segmentation of the posterior segment and often specifically the macular region. However, it may be possible to capture a cross-section of jCell using novel variants of OCT imaging in order to understand cell morphology. In order to image anterior vitreous or peripheral retinal locations where injected jCells may be located, an OCT instrument for anterior and posterior segment imaging will be used.

7.3.6 Full Field Scotopic Threshold Test (FST) (performed at jCyte Low Vision Facility)

Full-field stimulus threshold testing (FST) using LED-based ganzfeld stimulator (Colordome, Diagnosys LLC, Littleton, MA) can provide an estimation of which photoreceptor type (rod vs cone) is predominantly mediating light sensitivity. With serial FST assessments, changes in the retinal sensitivity of rods vs. cones in response to jCell therapy will be assessed. Blue and red stimuli can be used for testing monocularly under dark-adapted conditions.

8.0 SAFETY CONSIDERATIONS

8.1 Adverse Events

An AE is defined for this study as any untoward medical occurrence in a subject who is administered clinical study material. The occurrence of this event does not necessarily have a causal relationship with study product. An AE can therefore be any unfavorable and unintended sign (including an abnormal laboratory finding), symptom, or disease temporally associated with the use of a study (investigational) product or treatment (e.g. mock injection), whether or not related to the study product or treatment. CONFIDENTIAL 30 of 37 Examples of an AE include:

- Exacerbation of a chronic or intermittent pre-existing condition, including either an increase in frequency or intensity of the condition
- Significant or unexpected worsening or exacerbation of the condition/indication under study (RP)
- A new condition detected or diagnosed after study product administration even though it may have been present prior to the start of the study
- Signs, symptoms, or clinical sequelae of a suspected overdose of either study product or a concurrent medication
- Pre- or post-treatment events that occur as a result of protocol-mandated procedures
- Antibody development

An AE does **not** include:

- Medical or surgical procedures (e.g., colonoscopy or biopsy); the medical condition that leads to the procedure is an AE
- Social or convenience hospital admissions where an untoward medical occurrence did not occur
- Day-to-day fluctuations of a pre-existing disease or conditions present or detected at the start of the study that do not worsen
- The disease/disorder being studied (RP), or expected progression, signs, or symptoms of the disease/disorder being studied unless more severe than expected for the subject's condition

All AEs that occur after informed consent is signed will be recorded in the source documents and on the appropriate CRF page. The information to be collected includes the nature, date and time of onset, intensity (mild, moderate, severe, life-threatening, death), duration, causality (relationship to investigational product), and outcome of the event. Even if the AE/SAE is assessed by the Investigator as not reasonably attributable to study product, its occurrence must be recorded in the source documents and on the appropriate page of the CRF.

Treatment-emergent AEs will be defined as AEs that occur after the study treatment (injection or mock injection).

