1.0 INTRODUCTION

1.1 Background

1.1.1 Retinitis Pigmentosa

Retinitis pigmentosa (RP) refers to a group of inherited diseases causing retinal degeneration. The cell-rich retina lines the back inside wall of the eye. It is responsible for capturing images from the environment. People with RP experience a gradual decline in their vision because photoreceptor cells (rods and cones) die. Forms of RP and related diseases include Usher syndrome, Leber's congenital amaurosis, rod-cone degeneration, Bardet-Biedl syndrome, and Refsum disease, among others.

In most forms of RP, rods are affected first. Because rods are concentrated in the outer portions of the retina and are triggered by dim light, their degeneration affects peripheral and night vision. When the more centrally located cones - responsible for color and sharp central vision - become involved, the loss is in color perception and central vision. Night blindness is one of the earliest and most frequent symptoms of RP.

RP is typically diagnosed in adolescents and young adults. The classic clinical sign of the disease is the presence of dark deposits in the retina. The main risk factor is a family history of retinitis pigmentosa. It is an uncommon condition affecting about 1 in 4,000 people or roughly 100,000 individuals in the US¹. Cases of RP are associated with a wide variety of known gene mutations, with new mutations still being discovered. The mutations can be inherited from one or both parents or occur spontaneously; the pattern of inheritance can be autosomal recessive, autosomal dominant, X-linked or mitochondrial.

There is no effective treatment for RP; once photoreceptors are lost, they do not regenerate. The rate of deterioration of vision varies from person to person, with most people with RP legally blind by age 40. People with RP also often develop cataracts at an early age or swelling of the retina (retinal edema). Numerous breakthroughs in the treatment of cataract and corneal disease have greatly decreased the incidence of blindness from these causes. In contrast, treatment of retinal and optic nerve disease is more limited, with these conditions now representing major causes of incurable visual loss and a significant unmet medical need.

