3.2.2 Safety Endpoints

The main criteria that will be used to assess safety include:

- Incidence and severity of treatment-emergent adverse events (TEAE)
- Safety visual assessments: slit lamp and fundus exam, IOP

Blood samples will be collected from subjects at baseline and at designated times post-treatment to assess immunogenicity of the injected cells (PRA, DRA).

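### Significant but expected worsening of RP falls under two conflicting adverse-event rules, and no safety table counts vision loss independently of adverse-event reporting

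*Protocol*

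**What the plan says.** Protocol 8.1 gives examples of what is and is not an AE. The first list includes "Significant or unexpected worsening or exacerbation of the condition/indication under study (RP", and also "Exacerbation of a chronic or intermittent pre-existing condition, including either an increase in frequency or intensity of the condition". The second list removes the disease under study and its "expected progression, signs, or symptoms of the disease/disorder being studied unless more severe than expected for the subject's condition". Section 8.1 also requires an AE to be recorded even when the investigator does not attribute it to the product.

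Protocol 1.1.1 describes the course of the disease: "People with RP experience a gradual decline in their vision because photoreceptor cells (rods and cones) die". It adds that "The rate of deterioration of vision varies from person to person".

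Protocol 3.2.2 names the main safety criteria. The first is the incidence and severity of TEAEs; the second is slit lamp, fundus examination and intraocular pressure. Visual acuity and visual fields are secondary efficacy endpoints (Protocol 3.2.1 and 9.2; SAP 11.1). SAP 13.3, on ophthalmic safety, contains no acuity analysis, and the table index in SAP Appendix B places BCVA under efficacy data.

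**The concern.** The trial is single arm and asks whether a second injection into a previously treated eye is safe. Loss of sight in that eye is a harm the safety analysis should show directly. Among the listed safety criteria, only AE reporting can capture loss of vision itself, and for RP worsening that depends on a judgement about what was expected. Protocol 9.3 has AEs monitored by the investigator and the subject. No adjudication step is described, and there is no control arm in which the same judgement would be made.

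For other events, section 8.1 separates recording from attribution. For RP worsening, a view about cause can decide whether the event is recorded at all. An unrecorded loss reaches neither the TEAE tables nor serious-event reporting.

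**Working it through.** **1. The two rules side by side (Protocol 8.1).**

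| Worsening of RP | Inclusion example | Exclusion | Result |
|---|---|---|---|
| Unexpected | AE | does not apply | AE |
| Minor and expected | not met | applies | not an AE |
| Significant and expected | AE, because of the word *or* | applies | both rules met |

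The conflict is confined to the third row. The example about increased intensity of a chronic condition could also bring the second row into dispute.

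**2. Can the line be drawn?** The text available gives no letter-loss or field-loss threshold, no expected rate of decline and no fellow-eye rule. The exclusion's own limit, worsening more severe than expected, uses the same undefined yardstick.

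**3. Where would such a loss appear?** It would not be in the TEAE tables (14.3.2.x) if it is excluded. The ophthalmic safety tables (14.3.3.x) would show it only if a structural finding went with it. It would be in the BCVA summaries (14.2.1.1 and 14.2.1.2) and listings (16.2.4.1.1 and 16.2.4.1.2). Those summaries give number, mean, SD, median, minimum and maximum (SAP section 6), not a count of subjects who lost vision.

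**4. Size, for illustration only.** The plan states no event rate, so there is no figure to reproduce. The sample size, n = 25 to 30, is from the protocol synopsis and SAP section 5. Two inputs are assumed: p, the true proportion with important loss, and q, the share called expected.

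P(no recorded case) = [1 − p(1 − q)]^n

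- p = 10%, q = 0, n = 25: 0.90^25 = 0.072
- p = 10%, q = 50%, n = 25: 0.95^25 = 0.277
- p = 10%, q = 80%, n = 25: 0.98^25 = 0.603

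| p | n | q = 0 | q = 50% | q = 80% |
|---|---|---|---|---|
| 5% | 25 | 27.7% | 53.1% | 77.8% |
| 10% | 25 | 7.2% | 27.7% | 60.3% |
| 20% | 25 | 0.4% | 7.2% | 36.0% |
| 5% | 30 | 21.5% | 46.8% | 74.0% |
| 10% | 30 | 4.2% | 21.5% | 54.5% |
| 20% | 30 | 0.1% | 4.2% | 29.4% |

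In terms of a reported rate: 3 of 25 is 12.0% (exact 95% CI 2.5% to 31.2%). If all three were called expected, the AE table would show 0 of 25 (0% to 13.7%).

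**The case against.** The strongest reply is that vision loss is not lost from the report. BCVA is measured in both eyes at every visit and tabulated by eye with change from baseline, minimum and maximum. It is also listed by subject. Visual fields are tabulated by eye, and OCT tables cover macular edema, epiretinal membrane and traction. Visits from Day 1 to Month 9 ask about changes in vision. This stands, and it limits the point to how the safety analysis uses the data. It does not supply a count of subjects who lost vision, and a mean can conceal a few large losses.

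A second reply is that the rules mostly agree. Decline in RP is described as gradual, so a large loss within 12 months could be called more severe than expected. That is a reasonable reading, but the text does not oblige anyone to take it.

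A reader might infer three stronger things, none of which the documents support:

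- **That the bias can only favour safety.** Compared with recording every loss, the exclusion only removes events. But the chronic-condition example and the word *significant* could equally lead an investigator to record natural progression as a TEAE. The net direction is not shown.
- **That the re-injected eye is often the better eye.** The preference for the better-seeing eye applies only to subjects with both eyes previously treated, and the available text does not say how many those are.
- **That seven letters is a ready threshold for loss.** Protocol 7.2.4 uses it within one visit, "In the event that the two measurements differ by more than seven letters", to trigger a third measurement. It is not a limit for change between visits.

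The study procedure manual and part of the protocol's introduction were not available, so a definition there cannot be ruled out.

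**Conclusion.** The point holds in a limited form. Protocol 8.1 contradicts itself for RP worsening that is significant but expected. Vision loss placed in that category can be missing from the primary safety tables, while remaining in the efficacy summaries and listings. It would go too far to say that the two rules conflict throughout or that vision loss leaves the dataset.

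No size can be fixed from the documents. At an assumed 10% loss rate and n = 25, the chance of an AE table with no case runs from 7% with full recording to 60% if 80% of cases are called expected. Both inputs are assumptions, cases are treated as independent, and the plan ties no decision to seeing zero events. The remedy is worth making because it is cheap and bears directly on the primary question.

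**What to change.** 1. **Reconcile the two rules in Protocol 8.1** so that significant worsening in either eye is handled one way. Presumed cause belongs in the causality field and should not decide whether the event is recorded.

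2. **Add a table to SAP 13.3, shown beside Table 14.3.2.2**, derived from the existing BCVA data. It should count subjects with letter loss from baseline at several cut-offs, at each post-baseline visit and at the last visit, for study eye and non-study eye, with exact 95% confidence intervals. It should not depend on whether an AE was reported. The sponsor should set and justify the cut-offs. The number of eyes able to show each loss should be stated, since an eye scoring fewer letters at baseline than the cut-off cannot lose that many.

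The planned study period ended in Q3 2022 and the SAP is dated 09 Nov 2022, so rewording 8.1 may no longer change what was collected. The derived table is then the practical part. If the database is already locked, SAP section 6 requires it to be labelled post hoc.

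The cost is one table and a wording change. Some of the losses counted will be natural progression. The non-study eye is only a rough comparator, because it may itself have been treated before.
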